6.2.3 Efficacy Assessment Visits (9 Months and 18 Months)

Efficacy assessment will be performed on all patients at approximately 9 and 18 months (Days 253-272 and 553-560, respectively). Patients will not receive any study drug on these days.

As described in [Section 4.6](#), in consultation with the Investigator on Day 273 (+3 days), patients who meet the criteria for Rapid Disease Progression based on the 9-month efficacy assessments may continue study drug dosing or discontinue study drug dosing. Patients who discontinue study drug dosing may receive additional therapy for FAP, as per the local standard of care. These patients will remain on the study and follow the modified schedule of assessments shown in [Table 1-3](#) and described in [Section 6.4](#). Blinding will be maintained throughout.

The 9- and 18-month efficacy assessment visits will take place over 2 days.

- Perform the following efficacy assessments:

- mNIS+7*;
- NIS+7*;
- Timed 10-meter walk test*;
- Grip strength test*;

*Note: For the mNIS+7, NIS+7, timed 10-meter walk test, and grip strength test, an independent assessment will be performed on each day. Each site will make every effort to have these assessments performed by the same Investigator. Assessments are to be performed at least 24 hours (approximately) apart from each other but no greater than 7 days apart. For the mNIS+7 and NIS+7, components that are shared (including NIS and NCS) will be performed only once on each assessment day.

- PND score (see [Appendix 5](#));
 - FAP stage (see [Appendix 6](#));
 - If the patient has provided separate informed consent for the skin biopsies, obtain 2 sets of tandem 3-mm skin punch biopsies (4 biopsies total); 1 set from the distal lower leg when a patient's clinical status allows, and 1 set from the distal thigh. Skin biopsies will be performed at a CAS;
 - mBMI (Note: The site will only measure the patient's weight. Using this weight, mBMI will be calculated programmatically in the clinical database; the site will not perform the calculation.);
 - Echocardiogram;
 - Collect blood samples for NT-proBNP and troponin I;
 - Norfolk QOL-DN;
 - EQ-5D;
 - R-ODS;
 - COMPASS-31.
- Measure weight on both efficacy assessment days;
 - Measure vital signs on both efficacy assessment days;

- Complete the C-SSRS questionnaire;
- Complete the pharmacoeconomics questionnaire;
- Perform a 12-lead ECG;
- Collect blood samples for:
 - TTR protein, RBP, and vitamin A;
 - Additional aliquots of serum for long-term frozen storage, to permit testing of additional proteins related to FAP.
- Perform an ophthalmology examination (2 exams with 1 being completed between Days 231(\pm 3) and 272 at a CAS, and 1 completed between Days 546(\pm 3) and 560 at a CAS);
- Obtain information on concomitant medications;
- Document any AEs.

6.2.4 Follow-Up Visits

Patients will return to the study site for 2 follow-up visits, 21 days and 56 days after receiving their last dose of study drug. If a patient enrolls in the extension study, they will only have to complete the 21-day follow-up assessments (End of Study [EOS]; Day 567) and not the 56-day follow-up assessments (Day 602). Patients who do not enroll in the extension study will need to complete both follow-up visits (EOS [Day 567] and Day 602).

6.2.4.1 Twenty-One-Day Follow-up Visit (End of Study)

The following procedures will be performed at the 21-Day Follow-up visit (EOS; Day 567).

- Perform a physical examination;
- Measure weight;
- Measure vital signs;
- Collect blood sample for serum TTR protein, RBP, and vitamin A. Additionally, aliquots of serum samples will be taken for long-term frozen storage, to permit testing of additional proteins related to FAP;
- Perform a pregnancy test (for females of child-bearing potential only);
- Obtain information on concomitant medications;
- Document any AEs.

6.2.4.2 Fifty-Six-Day Follow-up Visit

This visit will only be conducted for patients who do not enroll in the extension study.

The following procedures will be performed at the 56-Day Follow-up visit (Day 602):

- Perform a physical examination;

- Measure vital signs;
- Collect blood sample for serum chemistry testing;
- Perform a pregnancy test (only for females of child-bearing potential);
- Obtain concomitant medications information;
- Document any AEs.

6.3 Early Withdrawal Visit and Follow-up Visits for Patients who Permanently Discontinue Study Treatment

6.3.1 Early Withdrawal Visit

For patients who withdraw early from the study, every effort will be made to have them return to the study site to have the following procedures performed. These visits will take place over 2 days.

- Perform the following efficacy assessments:
 - mNIS+7*;
 - NIS+7*;
 - Timed 10-meter walk test*;
 - Grip strength test*.

*Note: For the mNIS+7, NIS+7, timed 10-meter walk test, and grip strength test, an independent assessment will be performed on each day. Each site will make every effort to have these assessments performed by the same Investigator. Assessments are to be performed at least 24 hours (approximately) apart from each other but no greater than 7 days apart. For the mNIS+7 and NIS+7, components that are shared (including NIS and NCS) will be performed only once on each assessment day.

- PND score (see [Appendix 5](#));
- FAP stage (see [Appendix 6](#));
- If the patient has provided separate informed consent for the skin biopsies, obtain 2 sets of tandem 3-mm skin punch biopsies (4 biopsies total); 1 set from the distal lower leg when a patient's clinical status allows, and 1 set from the distal thigh;
- mBMI (Note: The site will only measure the patient's weight. Using this weight, mBMI will be calculated programmatically in the clinical database; the site will not perform the calculation.);
- Echocardiogram;
- Collect blood samples for NT-proBNP and troponin I;
- Norfolk QOL-DN;
- EQ-5D;

- R-ODS;
- COMPASS-31.
- Complete the pharmacoeconomics and C-SSRS questionnaires.
- Measure weight on both efficacy assessment days.
- Measure vital signs on both efficacy assessment days.
- Perform a physical examination.
- Collect a 12-lead ECG.
- Collect blood samples for clinical laboratory tests, including:
 - Hematology;
 - Serum chemistries;
 - Thyroid function tests;
 - Anti-drug antibody testing.
- Collect blood sample for serum TTR protein, RBP, and vitamin A. Additionally, aliquots of serum samples will be taken for long-term frozen storage, to permit testing of additional proteins related to FAP.
- Collect urine sample for urinalysis.
- Perform a pregnancy test (only for females of child-bearing potential).
- Collect a blood sample for plasma PK assessment;
- Collect a urine sample for PK assessment;
- Obtain information on concomitant medications;
- Document any AEs.

6.3.2 Follow-up Visits for Patients who Permanently Discontinue Study Treatment

Patients who permanently discontinue study treatment at any time after their first dose of study drug (due to decision made by treating physician or by the patient) may consent to return for follow-up visits at Months 9 and/or 18. If the patient discontinues study treatment >24 weeks prior to the Month 9 evaluation visit, the patient will complete follow-up visits at 9 and 18 months; if the patient discontinues study treatment after the Month 9 evaluation visit and >24 weeks before the Month 18 evaluation visit, the patient will complete a follow-up visit at 18 months.

These visits will take place over 2 days (at least 24 hours [approximately], but not more than 7 days apart). The following procedures will be performed:

- Perform the following efficacy assessments:
 - mNIS+7*;
 - NIS+7*;

*Note: For the mNIS+7 and NIS+7, an independent assessment will be performed on each day. Each site will make every effort to have these assessments performed by the same Investigator. Assessments are to be performed at least 24 hours (approximately) apart from each other but no greater than 7 days apart. For the mNIS+7 and NIS+7, components that are shared (including NIS and NCS) will be performed only once on each assessment day.

- PND score (see [Appendix 5](#));
 - FAP stage (see [Appendix 6](#));
 - mBMI (Note: The site will only measure the patient's weight. Using this weight, mBMI will be calculated programmatically in the clinical database; the site will not perform the calculation.);
 - Norfolk QOL-DN;
 - EQ-5D
- Perform a physical examination;
 - Measure weight on both efficacy assessment days;
 - Measure vital signs on both efficacy assessment days;
 - Collect blood sample for serum TTR protein, RBP, and vitamin A.
 - Determine Karnofsky Performance Status (see [Appendix 1](#));
 - Determine New York Heart Association classification of heart failure (see [Appendix 2](#));
 - Collect a blood sample for plasma PK assessment;
 - Collect data on subsequent FAP treatment regimens.

6.4 Modified Visit Schedule for Patients who Discontinue Study Drug for Rapid Disease Progression at Month 9

As described in [Section 4.6](#), in consultation with the Investigator, patients who meet the criteria for Rapid Disease Progression based on the 9-month efficacy assessments may continue study drug dosing or discontinue study drug dosing. Patients who discontinue study drug dosing may receive additional therapy for FAP, as per the local standard of care. These patients will remain on the study and follow a modified visit schedule as shown in [Table 1-3](#) and described in detail below. Blinding will be maintained throughout.

6.4.1 Modified Day 273

The following procedures will be performed on Day 273 (+3 days):

- Consult with the patient on a subsequent plan of care, which may include receiving therapy for FAP as per the local standard of care;
- Measure vital signs;

- Collect information on concomitant medications;
- Document any AEs.

Patients who discontinue treatment and also decide to discontinue from the study at the time of this visit will not have any additional visits after the Day 273 assessments are completed.

6.4.2 Modified Day 294

The following procedures will be performed:

- Perform a physical examination;
- Measure vital signs;
- Collect blood sample for serum chemistry testing;
- Collect blood sample for serum TTR protein, RBP, and vitamin A. Additionally, aliquots of serum samples will be taken for long-term frozen storage, to permit testing of additional proteins related to FAP;
- Collect a blood sample for plasma PK assessment;
- Collect a urine sample for PK assessment;
- Perform a pregnancy test (only for females of child-bearing potential);
- Obtain concomitant medications information (this will be the final collection of concomitant medications);
- Document any AEs (following this visit, only AEs that are considered related to study procedures will be collected);
- Collect data on subsequent FAP treatment regimens.

6.4.3 Modified Day 378 and Day 462

Study personnel will contact the patient by phone to query for general health status and data on subsequent FAP treatment regimens.

6.4.4 Modified Day 546

The following procedures will be performed:

- Perform a physical examination;
- Measure weight;
- Measure vital signs;
- Collect blood samples for clinical laboratory tests, including:
 - Hematology;
 - Serum chemistries and INR;
 - Thyroid function tests;
 - Anti-drug antibody testing.

- Collect urine sample for urinalysis;
- Perform a pregnancy test (only for females of child-bearing potential);
- Collect blood sample for serum TTR protein, RBP, and vitamin A. Additionally, aliquots of serum samples will be taken for long-term frozen storage, to permit testing of additional proteins related to FAP;
- Collect a blood sample for plasma PK assessment;
- Collect a urine sample for PK assessment;
- Complete the pharmacoeconomics questionnaire;
- Document any study-procedure-related AEs;
- Collect data on subsequent FAP treatment regimens.

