4.5.1 Reasons for Treatment Discontinuation or Withdrawal

The Investigator may discontinue treatment or withdraw a patient from the study if the patient:

- Is in violation of the protocol;
- Experiences a serious or intolerable AE;
- Becomes pregnant;
- Requires a prohibited medication (see [Section 5.8](#));
- Requests to discontinue treatment or be withdrawn from the study;
- Is found to be considerably noncompliant with the protocol-required patisiran dosing visits.

A patient may discontinue treatment or be withdrawn from the study if, in the Investigator's opinion, they are unable to continue. The Investigator will also withdraw the patient from the study upon the request of Alnylam, including if Alnylam terminates the study. Upon occurrence of a serious or intolerable AE, the Investigator will confer with Alnylam before discontinuing treatment.

In general, patients who discontinue treatment will be encouraged to remain on the study to complete study assessments, particularly the Month 9 and Month 18 assessments, so that their experience is captured in the final analyses. However, a patient may withdraw consent to participate in the study at any time.

Missing an occasional dose of study drug will not necessarily result in the patient being withdrawn from the study. However, if a patient misses 2 consecutive doses of study drug, the Investigator at the site and the Medical Monitor will determine whether treatment should be discontinued.

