6.2.2 Routine Study Visits

The procedures described below are to be performed for all routine study visits (from Day 21 through Day 546), with the exception of the 9-month and 18-month efficacy assessments (occurring on Days 253-272 and Days 553-560, respectively). All visits have a window of "±3 days" except for the Day 273 visit which has a window of "+3 days" to allow adequate time for the assessment of the patient's 9-month mNIS+7 and FAP stage testing, which will determine if the patient met the criteria for Rapid Disease Progression.

Patients will undergo the following procedures before study drug dosing:

- At all dosing visits, administer premedications at least 60 minutes prior to the start of administration of study drug (see [Section 5.3.1](#));
- At all dosing visits, measure weight;
- At all dosing visits, measure vital signs;

- On Days 252 and 546, perform a physical examination;
- On Days 126 and 399, perform a 12-lead ECG;
- On Days 21, 126, 252, 273, 399, and 546, collect blood sample for serum TTR protein, RBP, and vitamin A. Additionally, aliquots of serum samples will be taken for long-term frozen storage, to permit testing of additional proteins related to FAP;
- On Days 84, 189, 357, 462, and 546, collect blood samples for serum chemistry tests;
- On Day 546, collect blood sample for INR;
- On Days 21, 126, 252, 399, and 546, collect a blood sample for anti-drug antibody assessment;
- On Days 252 and 546, collect blood samples for clinical laboratory tests, including:
 - Hematology;
 - Thyroid function tests.
- On Days 252 and 546, collect urine sample for urinalysis;
- On Days 21, 126, 252, 399, and 546, collect a plasma PK sample pre-dose (within 1 hour of planned study drug dosing);
- On Days 21, 126, 252, 399, and 546, collect a urine PK sample pre-dose (within 1 hour of planned dosing start);
- Perform ophthalmology examinations on Day 21 (if baseline examination was not completed prior to the Day 21 visit), once between Days 231(\pm 3) and 272 at a CAS, and once between Days 546(\pm 3) and 560 at a CAS;
- Complete the pharmacoeconomics questionnaire on Day 21, if not completed prior to the Day 21 visit;
- At all dosing visits, obtain information on concomitant medications;
- At all dosing visits, document any AEs.

Following the completion of all required pre-dose activities and assessments, administer the study drug at all dosing visits, as described in [Section 6.2.1.2](#).

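### Patients who stop drug but stay on study have mBMI scheduled at Month 18 with no albumin drawn, so the value is missing by design; they also have no scheduled off-drug hematology or urinalysis

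*Protocol*

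**What the plan says.** Protocol 4.5 lets a patient stop drug and remain in the study, and 4.5.1 says that "patients who discontinue treatment will be encouraged to remain on the study to complete study assessments". For stops other than rapid progression at Month 9, section 6.3.2 governs: such patients "may consent to return for follow-up visits at Months 9 and/or 18". The visits include mNIS+7, Norfolk QOL-DN, weight and mBMI. The only blood drawn is for TTR, RBP, vitamin A and plasma PK. The two matching columns of Table 1-2 also show no chemistry, hematology or urinalysis.

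Protocol 7.2.5 and SAP 1.1.2.2 define mBMI as BMI multiplied by serum albumin. Albumin belongs to the chemistry panel (7.5.5). Section 6.2.2 ties that panel to dosing visits on Days 84, 189, 357, 462 and 546. SAP 4.3.2 uses those five days for mBMI and takes Day 546 as Month 18. SAP 3.8 includes efficacy data from after treatment discontinuation; SAP 3.8.3 leaves missing values unimputed under a missing-at-random assumption.

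For safety samples, 6.2.2 says "On Days 252 and 546, collect urine sample for urinalysis", with hematology on the same two days. Section 6.2.4 provides "2 follow-up visits, 21 days and 56 days after receiving their last dose of study drug" but labels them Days 567 and 602; only the second includes chemistry, and neither includes hematology or urinalysis. The full panel in 6.3.1 is tied to leaving the study: "For patients who withdraw early from the study, every effort will be made to have them return to the study site".

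**The concern.** The protocol asks for an endpoint at a visit where one of its two ingredients is not collected. The patient attends, is weighed and gives blood, yet the Month 18 mBMI cannot be formed as the SAP specifies. The MMRM then projects the off-drug Month 18 value mainly from that patient's on-drug values, which is not what SAP 3.8 sets out to capture. No sensitivity analysis of mBMI is planned that would test the assumption (SAP 5.6). Patients who stop for rapid progression do not have this problem: their modified Day 546 visit (6.4.4) collects both weight and chemistry.

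The second part concerns safety. The patients whom 4.5.1 encourages to stay, including those who stop for an adverse event, get less scheduled laboratory follow-up than patients who leave. At stake are a small, avoidable loss in one ranked secondary endpoint and a lack of routine off-drug laboratory values.

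**Working it through.** The plan gives no figure to reproduce here, so this is a schedule check.

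**Inputs.** Dosing is every 21 days from Day 0 to Day 546: 546/21 + 1 = 27 doses. Chemistry days after Day 0 are 84, 189, 357, 462 and 546; hematology and urinalysis days are 252 and 546 (6.2.2). The Month 18 visit is on Days 553 to 560, ±10 days for this group; the 56-day visit is ±10 days and the 21-day visit ±7 days (Table 1-2). The 24-week rule in 6.3.2 is 24 × 7 = 168 days. I date the stop from the last dose.

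**Who falls under the 24-week rule.** 553 − 168 = 385 and 560 − 168 = 392. The last dosing day before both is Day 378; the next is Day 399.

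**Albumin at the SAP's five post-baseline mBMI days:**

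| Last dose | Days with albumin | Count of 5 | Day 546 (Month 18) |
|---|---|---|---|
| 0 to 63 | none | 0 | missing |
| 84 to 168 | 84 | 1 | missing |
| 189 to 336 | 84, 189 | 2 | missing |
| 357 to 378 | 84, 189, 357 | 3 | missing |

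**Can the 56-day chemistry supply the albumin?**

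- *Timed from the actual last dose:* it falls at most 56 + 10 = 66 days after that dose. The stop is more than 168 days before Month 18, so the sample is more than 168 − 66 = 102 days before the visit. With a last dose on Day 378, the latest sample is Day 444, and 553 − 444 = 109 days.
- *Fixed at Day 602:* 602 − 560 = 42 and 602 − 553 = 49, so 6 to 7 weeks after the nominal Month 18 visit. Day 602 is not an SAP mBMI time point.

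The 56-day visit takes no weight on either reading. By comparison, a patient still on drug has albumin on Day 546, 553 − 546 = 7 days before the efficacy visit. That is why listing mBMI without chemistry at the ordinary 18-month visit (6.2.3) does no harm.

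**Hematology and urinalysis.** Doses through Day 231 number 231/21 + 1 = 12 of 27.

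| Patient | Scheduled on drug, after baseline | Scheduled off drug |
|---|---|---|
| Stays on study, last dose by Day 231 | 0 | 0 |
| Stays on study, last dose Days 252 to 525 | 1 (Day 252) | 0 |
| Leaves study, last dose by Day 231 | 0 | 1 (Early Withdrawal) |
| Stops for rapid progression, last dose Day 252 | 1 (Day 252) | 1 (Day 546, 546 − 252 = 294 days later) |

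**The case against.** The strongest reply is that 6.3.2 is a voluntary, deliberately light visit built around mNIS+7 and Norfolk QOL-DN, and that clinical need is met elsewhere. Much of this stands.

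- **A reader might infer that patients who stop for an adverse event go unmonitored.** The documents do not support that. Unscheduled visits are allowed (6.5), clinically relevant abnormal results should be repeated and followed (7.5.5), and serious events call for laboratory work as needed (8.11). SAP 3.9 lets unscheduled results enter the shift tables. What is missing is a routine draw.
- **A reader might blame 6.3.2 for the zero count up to Day 231.** Every patient, including those still on drug, has no scheduled post-baseline hematology or urinalysis before Day 252. Section 6.3.2 adds only the lack of an off-drug sample.
- **A reader might conclude that Month 18 mBMI is lost for every patient who stops before Day 546.** The case is not established for last doses on Days 399 to 525. Section 6.3.2 does not say which visits they complete. Timed from the last dose, their 56-day chemistry would fall on Days 455 to 581 (399 + 56; 525 + 56), some of it close to Day 546.
- **A reader might ask for a full safety panel at Month 18.** More than 24 weeks off drug, it lies far outside the SAP's 28-day treatment-emergent window and would tell little.

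It is also true that neither document limits how far apart weight and albumin may be, so a Day 602 albumin could in principle be paired with a Month 18 weight. No rule provides for that, however. The three-month grouping in SAP 3.9 covers unscheduled and discontinuation visits, not scheduled follow-up. Finally, the MMRM uses all mBMI time points, so earlier values still contribute. That softens the loss but does not supply an off-drug Month 18 value.

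**Conclusion.** The point holds for patients who stop drug for reasons other than rapid progression, more than 24 weeks before Month 18, and who return. Section 6.3.2 followed exactly gives them no Month 18 mBMI as the SAP defines it, on either reading of the 56-day visit. The absence of scheduled off-drug hematology and urinalysis also holds, as a secondary matter.

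The effect is minor. The primary analysis is not touched, mBMI is fifth in the secondary hierarchy, and laboratory summaries are descriptive. The number of patients is unknown. The only planning figure is 25% premature discontinuation (0.25 × 200 = 50), which does not separate stopping drug from leaving the study.

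The conclusion assumes that patients off drug do not attend dosing visits, that stops are dated from the last dose, and that no unscheduled chemistry is drawn near Month 18.

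**What to change.** 1. Add a serum chemistry tube (for albumin) to the existing Month 18 blood draw in Protocol 6.3.2 and Table 1-2. State in SAP 4.3.2 that for this group that visit supplies the Month 18 mBMI. Its window, Days 543 to 570, runs from 3 days before to 24 days after Day 546. No tube is needed at Month 9, which is not an SAP mBMI time point.
2. State in 6.2.4 that for this group the 21- and 56-day visits run from the actual last dose. Add chemistry, hematology and urinalysis to the 21-day visit. At 21 ± 7, or 14 to 28 days, it lies within the SAP's 28-day treatment-emergent window.

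A Month 18 hematology tube is not worth adding.

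The cost per patient is one tube at Month 18, and two tubes and a urine sample at the 21-day visit, in a group of unstated size. Blood is already drawn at both visits. No new visit is needed if 6.2.4 already applies to this group; otherwise there are two short ones. Item 1 deserves priority, because it repairs a ranked endpoint at almost no cost. Because SAP 5.4 reports enrollment complete, added samples help only patients whose relevant visits are still to come.
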